#### **11.4 Data and Safety Monitoring Board**

The responsibility for reviewing the ethical conduct of the study and for monitoring reports of evidence of adverse or beneficial effect is assigned to the DAIT Autoimmunity DSMB. The DSMB is an independent group composed of biomedical ethic experts, physicians, and other scientists who are responsible for continuing review of study information. The DSMB makes recommendations to DAIT, NIAID on issues affecting the course and conduct of this clinical study.

#### **11.5 Study Termination**

In the event that the study is terminated, subjects who have received study treatment will be followed for the study's three years of safety follow-up.

### **12 FINANCING AND INSURANCE**

Participating institutions must comply with their institution's policies on compensation, insurance, and indemnity. Institutions must have adequate liability insurance coverage to satisfy their local and national requirements for study participation.

### **13 PUBLICATION POLICY**

The ACE policy on publication of study results will apply to this study. Authorized participants may find details regarding the policy statement on the ACE internet website [REDACTED]. Study investigators are encouraged to communicate and publish study results with prior notification of DAIT, NIAID. The following procedure is suggested:

1. Manuscripts, abstracts, posters and other material for public distribution will be submitted to DAIT, NIAID at least 30 days prior to submission for publication or public presentation.
2. DAIT, NIAID will review and comment on the proposed material within 30 days.
3. DAIT, NIAID may ask that confidential information be deleted or redacted in this case where a patent may be filed or where confidential information is involved. Publication

or presentation may be delayed up to 60 additional days in order to file a patent application.

## 15 APPENDICES

- 15.1: PDAI
- 15.2: Skindex-29 (version 2)
- 15.3: Patient's Global Assessment
- 15.4: Physician's Global Assessment
- 15.5: Subject Self-Reported Demographics Optional Source Document
- 15.6: Pre-Infusion Required Checklist

**15.1 PDAI**

Pemphigus Disease Area Index (PDAI) [71]: The PDAI was developed by consensus by the International Pemphigus Definitions Committee in 2008 [58] PDAI consists of total sum of scores for Activity and Damage for skin and scalp, and Activity alone for mucous membrane. The maximum total activity score is 250 and maximum damage score is 13; the maximum total PDAI score is 263. The PDAI was found to be more reproducible than the ABSIS in a recent study of 15 patients with pemphigus [72]. PDAI also correlated more closely with Physician Global Assessment score [72]. It is considered to be a reliable tool for clinical trials as it is able to detect small differences in patients with mild or partially treated disease [71].

**Pemphigus Disease Area Index (PDAI)**

Skin		Activity	Damage
Anatomical Location	Erosion/Blisters or new erythema		Post-inflammatory hyperpigmentation or erythema from resolving lesion
	0 absent 1 1-3 lesions, up to one >2 cm in any diameter, none > 6 cm 2 2-3 lesions, at least two > 2 cm diameter, none > 6cm 3 >3 lesions, none > 6 cm diameter 5 >3 lesions, and/or at least one >6 cm 10 >3 lesions, and/or at least one lesion >16 cm diameter or entire area	Number lesions if ≤ 3	0 absent 1 present
Ears			
Nose			
Rest of the face			
Neck			
Chest			
Abdomen			
Back, buttocks			
Arms			
Hands			
Legs			
Feet			
Genitals			
Total skin	/12		2
Scalp			
Scalp	Erosion/Blisters or new erythema		Post-inflammatory hyperpigmentation or erythema from resolving lesion
	0 absent 1 in one quadrant 2 two quadrants 3 three quadrants 4 affects whole skull 10 at least one lesion > 6 cm		0 absent 1 present
Total Scalp (0-10)	/10		/1
Mucous membrane			
Anatomical Location	Erosion/Blisters		
	0 absent 1 1 lesion 2 2-3 lesions 5 >3 lesions or 2 lesions >2 cm 10 entire area	Number lesions if ≤ 3	
Eyes			
Nose			
Buccal mucosa			
Hard palate			
Soft palate			
Upper gingiva			
Lower gingiva			
Tongue			
Floor of mouth			
Labial mucosa			
Posterior pharynx			
Anogenital			
Total Mucosa	/120		
Total Activity Score:			Total Damage Score 

©2007 by the authors

## 15.2 Skindex-29 (version 2) [62]

The Skindex-29 is a skin-specific quality of life (QoL) tool consisting of 29 items that measure patient symptoms, emotions, and function [58].

APG01: PolyTraps for Pemphigus

Required Source Document

Manual of Procedures

**SUBJECT SOURCE DOCUMENTATION  
FOR THE  
SKINDEX29 DERMATOLOGY SURVEY**

**SAMPLE**  
Subject ID #: \_\_\_\_\_

**Subject Instructions:**

[figure not shown]
Please complete the attached survey and return it to your APG01 Study Coordinator.  
Please initial and date this form as indicated.

[figure not shown]
Subject Initials: \_\_\_\_\_

[figure not shown]
Date survey completed: \_\_\_\_\_

APG01: Skindex29 Required Source Document

06 September 2016

### 15.3 Patient's Global Assessment

APG01: PolyTregs for Pemphigus

[figure not shown]
Required Source Document

Manual of Procedures

#### PATIENT'S GLOBAL ASSESSMENT: (3in)

Subject ID #: \_\_\_\_\_

#### EXAMPLE

**SAMPLE**  
YOUR RESPONSE:

Please rate your current pemphigus disease activity on the scale below, with 0 being no disease activity and 3 being severe disease activity.

----- **For Site Coordinator Use Only** -----

**Site Coordinator Directions:** Using the markings provided, measure from the "0" to the vertical line placed by the subject. Enter the distance in inches as indicated below, then transfer the pertinent information onto the appropriate eCRF page, and place this document in the subject's research record.

Length of line  
(from 0 to vertical assessment line) \_\_\_\_\_ in (per markings provided)

Initials of site personnel measuring the line: \_\_\_\_\_ Date: \_\_\_\_\_

### 15.4 Physician’s Global Assessment

APG01: PolyTregs for Pemphigus

Required Source Document

[figure not shown]
Manual of Procedures

#### PHYSICIAN’S GLOBAL ASSESSMENT:

(3in)

Subject ID #: \_\_\_\_\_

#### EXAMPLE

SAMPLE

YOUR RESPONSE:

Please rate the patient’s current pemphigus disease activity on the scale below, with 0 being no disease activity and 3 being severe disease activity.

----- For Site Coordinator Use Only -----

**Site Coordinator Directions:** Using the markings provided, measure from the “0” to the vertical line placed by the physician. Enter the distance in inches as indicated below, then transfer the pertinent information onto the appropriate eCRF page, and place this document in the subject’s research record.

Length of line  
(from 0 to vertical assessment line) \_\_\_\_\_ in (per markings provided)

Initials of site personnel measuring the line: \_\_\_\_\_ Date: \_\_\_\_\_

### 15.5 Subject Self-Reported Demographics Optional Source Document

# SAMPLE

APG01: Poly/Tregs for Pemphigus

Optional Source Document

Manual of Procedures

## SUBJECT SELF-REPORTED DEMOGRAPHICS OPTIONAL SOURCE DOCUMENT

*Rave EDC Folder: Screening*

*Rave EDC Page: Demography*

**Subject ID #:** \_\_\_\_\_

**Subject instructions:** Please complete the survey by checking the box or boxes that most closely identify your race and ethnicity. Check multiple boxes if necessary. Initial and date this form as indicated and return it to your APG01 Study Coordinator.

**Date of Birth:** \_\_\_\_\_ **Gender:**  Male  Female  
MM/DD/YYYY

**Ethnicity:**  Hispanic or Latino  Not Hispanic or Latino

**Race:**

**White:**

- White, not otherwise specified
- Eastern European
- European, not otherwise specified
- Mediterranean
- Middle Eastern
- North Coast Of Africa
- Western European
- White Caribbean
- White North American
- White South or Central American

**Black or African American:**

- Black, not otherwise specified
- African American
- African Black (both parents born in Africa)
- Caribbean Black
- South or Central American Black

**Other:**

- Unknown
- Other, specify:

**Asian:**

- Asian, not otherwise specified
- Asian Indian/South Asian
- Chinese
- Filipino
- Guamanian
- Korean
- Japanese
- Vietnamese
- Other Southeast Asian

**Native Hawaiian or Other Pacific Islander:**

- Hawaiian
- Native Pacific Islander, not otherwise specified
- Samoan

**American Indian or Alaska Native:**

- Native American, not otherwise specified
- American Indian, not otherwise specified
- Caribbean Indian
- Native Alaskan/Eskimo/Aleut
- South or Central American Indian

Subject Initials: \_\_\_\_\_

Date survey completed: \_\_\_\_\_

APG01: Demographics Optional Source Document

06 September 2016

### 15.6 Pre-Infusion Required Checklist

APG01: PolyTregs for Pemphigus

Required Source Document

Manual of Procedures

#### APG01 PRE-INFUSION REQUIRED CHECKLIST

Complete this form in preparation for the PolyTreg Infusion for all subjects who have a Baseline (Day 0) visit.  
Please note that all steps listed here must be completed before the start of the infusion.

Subject ID #: \_\_\_\_\_

Procedures/Steps Answer to each item must be Yes or N/A as applicable to proceed with the PolyTreg infusion.	Yes	No	N/A
1. Subject's medical history has been updated & does not meet any Criteria for Withholding Study Treatment (Protocol Section 5.3.4) .			
2. Subject's concomitant medication record has been updated & does not contain prohibited medications as per Protocol Section 5.7 .			
3. Adverse Event assessment has been completed and does not meet any Criteria for Withholding Study Treatment (Protocol Section 5.3.4) .			
4. Pre-Infusion Physical Examination with Vital Signs has been conducted with no findings meeting Criteria for Withholding Study Treatment (Protocol Section 5.3.4) .			
5. All baseline assessments as per Protocol Table 6.1, Schedule of Events , have been completed. This includes PDAI, desmoglein 1/3, Skindex-29, Physician's Global Assessment, Patient's Global Assessment, Digital Photography of lesions, & urinalysis with microscopic analysis.			
6. PDAI total score is between, and inclusive of, 1 to 12.			
Laboratory Assessments			
7. Subject's Day 0 urine pregnancy test is negative (if woman of childbearing potential).			
8. Subject's Day 0 Hematology Panel has been drawn, reviewed, and confirmed to not meet any Criteria for Withholding Study Treatment (Protocol Section 5.3.4) . Hematology Panel includes a CBC with differential and platelets.			
9. Subject's Day 0 Chemistry Panel has been drawn, reviewed, and confirmed to not meet any Criteria for Withholding Study Treatment (Protocol Section 5.3.4) . Chemistry Panel includes BUN, creatinine, AST, ALT, total bilirubin, direct bilirubin, ALK, albumin, sodium, potassium, chloride and bicarbonate.			
Infusion Eligibility			
If any of the above criteria 1-9 have been checked as "No" then the subject is ineligible to receive the PolyTreg infusion.			
I have reviewed the above elements and confirm the subject is eligible to proceed with the PolyTreg Infusion			
Investigator Signature _____	Date _____	Time _____	AM  PM 
If No, specify exclusion below: 
SAMPLE
			
Comments:			
Continue Pre-Infusion Checklist on next page			

APG01: PolyTregs for Pemphigus

Required Source Document

Manual of Procedures

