### 1.6.3 Rationale for the Selection of the Patient Population

This phase I trial is being conducted in subjects with pemphigus for two principal reasons. First, the selection of this population allows us to examine the impact of PolyTreg therapy not only in the peripheral blood, but also in the skin in patients with pemphigus. Mild to moderately active disease is being targeted in this phase I safety study, with a PDAI severity score of 3-10 being required for screening (with activity score no higher than 12 at time of PolyTreg infusion) [56, 57]. Second, cutaneous manifestations of pemphigus can be severe, refractory, and life-threatening, with significant insensible losses and impaired barrier function leaving patients susceptible to serious infections. Therefore, this patient population warrants examination of a novel therapy that would be of utility if the treatment proves to have a favorable risk:benefit ratio.

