### 4.1 Inclusion Criteria

Subjects who meet all of the following criteria are eligible for enrollment into the study:

1. Ability to provide informed consent
2. Age 18-75 years at Screening Visit
3. Diagnosis of PV or PF, defined by H&E and direct immunofluorescence staining of skin biopsy at any time prior to enrollment
4. Pemphigus treated with systemic corticosteroids within the 2 years prior to screening (historic or current) or treated with rituximab at least 12 months prior.
5. Presence of:
  - a. anti-Dsg3 antibodies (>20.0 U/ml) at screening visit consistent with diagnosis of pemphigus vulgaris, or
  - b. anti-Dsg1 antibodies (>20.0 U/ml) at screening visit consistent with diagnosis of pemphigus foliaceus
6. Active PV or PF as defined by PDAI overall activity score 3-10 at screening visit, and PDAI overall activity score 1-12 at baseline visit
7. Positive test for EBV antibody
8. Adequate venous access to support draw of 400 ml whole blood and infusion of investigational therapy
9. An absolute Treg count of  $\geq 42$  cells/ $\mu$ L within 6 weeks prior to whole blood collection at Week -2

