#### 5.3.4 Criteria for Withholding Study Treatment

Infusion of study product is to be withheld if the subject is experiencing any of the following on the day of infusion:

- Fever > 38.0°C
- Acute Diarrhea and/or Vomiting
- Other signs/symptoms of an intercurrent NCI-CTCAE Grade 2 or higher infection.
- Significant pemphigus relapse/flare (PDAI >12)
- Other elements precluding infusion as per the study pre-infusion checklist (see Section 15.6, *Pre-Infusion Required Checklist*)
- Other comorbid conditions which in the opinion of the investigator would pose risk to the subject with administration of the study product

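### Checklist item 6 sets the Day 0 PDAI limit of 1-12 on the total score, whereas inclusion criterion 6 sets it on the activity score

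*Combined protocol and SAP*

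**What the plan says.** Four places in the combined protocol bear on the PDAI limit on the day of infusion.

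- **Inclusion criterion 6** (synopsis and Section 4.1) requires an overall activity score of 3-10 at screening and then "PDAI overall activity score 1-12 at baseline visit".
- **Section 1.6.3** describes the population in the same terms: "with activity score no higher than 12 at time of PolyTreg infusion".
- **Section 5.3.4** lists, among the reasons to withhold infusion, "Significant pemphigus relapse/flare (PDAI >12", with no component named.
- **Section 15.6, checklist item 6**, requires that "PDAI total score is between, and inclusive of, 1 to 12".

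Section 15.1 defines the index as a sum of activity and damage scores and gives the ranges: "The maximum total activity score is 250 and maximum damage score is 13; the maximum total PDAI score is 263". The damage column of the scoring sheet records "Post-inflammatory hyperpigmentation or erythema from resolving lesion".

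The checklist is labelled a required source document. Its header says "Answer to each item must be Yes or N/A as applicable to proceed with the PolyTreg infusion", and item 6 has no N/A box. If any of items 1-9 is answered No, "then the subject is ineligible to receive the PolyTreg infusion". The protocol body adopts the form: Section 5.3.1 says it will be used before infusion, and Section 5.3.4 makes the elements on it grounds for withholding.

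**The concern.** The same range, 1-12, is attached to two different quantities. Criterion 6 and Section 1.6.3 count only active lesions. Item 6 as worded also counts marks left by resolving lesions. Such marks are plausible here, because criterion 4 requires earlier treatment with systemic corticosteroids or rituximab. Screening sets no limit on damage, so a conflict between the two rules would first appear on Day 0.

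By then the subject has given 400 ml of blood and a 14-day expansion has produced a fresh, non-cryopreserved autologous product (Section 5.1.1). After a missed infusion, Section 5.4 allows repeat screening no sooner than 8 weeks after the donation. If the second donation falls within 12 weeks of the first, only hematology and the EBV/CMV viral load must be repeated, so PDAI need not be rechecked beforehand. Damage that persists could then cause a second refusal, and Section 5.5.3 withdraws a subject who has donated twice without being infused. The trial infuses at most 12 subjects at about four sites and already reports low PolyTreg yield (Section 1.6.2), so even one needless refusal would be costly.

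**Working it through.** **1. Reproduce the ranges in Section 15.1 from the scoring sheet.**

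- Activity: 12 skin sites × 10 + scalp 10 + 12 mucosal sites × 10 = 120 + 10 + 120 = 250.
- Damage: 12 skin sites × 1 + scalp 1 = 13.
- Total: 250 + 13 = 263.

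All three figures match. In Section 15.1 the total PDAI score therefore means activity plus damage.

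**2. Write the two rules with A = activity and D = damage (0-13).**

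- Criterion 6 at baseline: 1 ≤ A ≤ 12.
- Item 6 read literally: 1 ≤ A + D ≤ 12.

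**3. Upper end.** A subject who meets criterion 6 fails item 6 when A + D ≥ 13, that is, when D ≥ 13 − A.

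| Activity | Damage that turns item 6 to No |
|---|---|
| 3 | 10 or more |
| 8 | 5 or more |
| 10 | 3 or more |
| 12 | 1 or more |

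A subject with activity 10 and damage 3 passes screening. With unchanged disease, the same subject has a total of 13 on Day 0 and is refused.

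**4. Lower end.** With A = 0 and D from 1 to 12, A + D lies between 1 and 12. Item 6 is met and criterion 6 is not. Section 5.3.4 has no lower limit, so item 6 is the only checklist item that tests one.

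**5. Direction of the error at the upper limit.** Since D ≥ 0, A + D ≤ 12 implies A ≤ 12. The literal reading is never more permissive than criterion 6 at the top of the range.

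**6. Extent of the mismatch in possible scores.** Criterion 6 admits 12 × 14 = 168 pairs (A, D). Those that also satisfy item 6 number 12 + 11 + … + 1 = 78, so 168 − 78 = 90 pairs meet criterion 6 and fail item 6. Another 12 pairs (A = 0, D = 1-12) do the reverse. If item 6 is read on activity, the two rules coincide and no pair is discordant. These are counts of possible scores, not proportions of patients.

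**The case against.** The strongest reply is that the documents show what was intended. Every statement in the protocol body that names a component for the Day 0 limit names activity, and no section sets a limit on activity plus damage. Section 15.1 uses the word total for the activity score as well as for the full index. The scoring sheet has sum boxes for total activity and total damage but none for the combined score, so a coordinator applying item 6 literally would have to compute a figure that the sheet does not request. The bullet in Section 5.3.4 concerns flare, which the protocol defines by new or extending lesions, and stable pigmentation is not a flare. The checklist is also visibly unfinished. It is stamped as a sample, carries a placeholder for a Manual of Procedures section, and points to Section 5.5.5 for biopsies (they are in 5.6.5) and to 5.7 for prohibited medications (they are in 5.8).

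All of this stands as evidence of intent, and it is why activity is taken here as the intended meaning. It does not change what item 6 says, and a form that must be answered Yes before infusion should not depend on inferred intent. Section 5.3.1 says infusion may be held on the checklist at the investigator's discretion. That is hard to square with the form's own ineligibility rule, and it leaves sites room to differ.

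Two stronger readings are tempting, and the documents support neither. A reader might infer that the mismatch does change who is infused. That would require the final form to keep this wording and a site to apply it literally, and neither the final form nor the Manual of Procedures is in the file. A reader might also turn the pair counts, or an assumed damage distribution, into an expected number of refusals. Suppose each of the 13 damage sites is marked independently with probability q and activity is uniform on 3-10. Then the share failing item 6 with unchanged scores is 0.3% at q = 0.05 and 25% at q = 0.3, or about 0.04 to 3.0 per 12 subjects. The answer follows the assumed q, on which the documents are silent, and it also presumes a literal reading at every site.

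**Conclusion.** The point holds as a decision threshold that is wrong as written in an appended required form. Its severity is modest. The texts conflict, nothing in the file reconciles them, and the protocol body gives the checklist force. Taken literally, item 6 errs in two ways: it can refuse an eligible subject who has residual damage, and it can pass a subject with no activity who fails criterion 6. In the second case criterion 6 still applies and should stop the infusion if it is checked separately.

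The conclusion rests on reading the total score as Section 15.1 uses it and on the appended form resembling the one that sites use. The frequency of either error cannot be estimated from the documents. The upper limit on activity is never relaxed, so there is no added exposure of subjects with more active disease. The definition of the primary endpoint and the probabilities in Table 8.1 are untouched.

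**What to change.** In checklist item 6, replace *total score* with *overall activity score* and keep the range 1 to 12 inclusive. In the flare bullet of Section 5.3.4, write *PDAI overall activity score* in place of the bare *PDAI*, keeping the threshold of more than 12. Carry the same wording into the operative form in the Manual of Procedures.

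If the sponsor does want a limit on activity plus damage, it belongs in inclusion criterion 6 and should also be applied at screening, so that a subject who would fail on damage is identified before the donation.

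The cost is two phrases. The scoring sheet already records activity and damage separately, so no assessment, visit or analysis changes.

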**APG01 PRE-INFUSION REQUIRED CHECKLIST**

Complete this form in preparation for the PolyTreg Infusion for all subjects who have a Baseline (Day 0) visit.  
Please note that all steps listed here must be completed before the start of the infusion.

Subject ID #: \_\_\_\_\_

Baseline Mechanistic Assessments: To be obtained after eligibility has been confirmed above Answer to each item must be Yes or N/A as applicable to proceed with the PolyTreg infusion.	Yes	No	N/A
10. Three skin biopsies were obtained and processed per Protocol Section 5.5.5 and MOP Section XX .			
11. Lymphocyte subsets were drawn (3mL in lavender top EDTA tube).			
12. Mechanistic specimens were drawn (20mL in two green top sodium heparin tubes).			
Certificate of Analysis/Chain of Custody Documentation			
13. Upon receipt of the subject's Treg product for infusion from the HICTF, the Interim Certificate of Analysis and the product's Chain of Custody have been reviewed and signed.			
Comments:  
SAMPLE
			

Signature/Initials: \_\_\_\_\_ Date: \_\_\_/\_\_\_/\_\_\_
